7. RESEARCH QUESTION AND OBJECTIVES

This study aims to evaluate the efficacy of Enbrel as a biological treatment in moderate-to-severe plaque psoriasis patients in Iraq.

Primary objective: Efficacy of Enbrel in patients with moderate-to-severe plaque psoriasis by measuring baseline BSA, PASI, and DLQI scores compared to BSA, PASI, and DLQI scores after 6 months of initiation of treatment and compared to the last visit follow-up BSA, PASI, and DLQI scores.

Secondary objective:

Determine the first year adherence of patients with moderate-to-severe plaque psoriasis on a Enbrel treatment.

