8. RESEARCH METHODS

8.1. Study Design

This is a retrospective analysis of approximately 400 Iraqi patients diagnosed with moderate-to-severe plaque psoriasis that received Enbrel as treatment for disease.

Baseline, 6 months after initiation of Enbrel treatment and last visit follow-up, BSA, PASI, and DLQI scores for identified patients will be collected and used to evaluate efficacy. Patients will be further divided into 2 groups according to their adherence to Enbrel treatment (The adherent group will include the patients who were adherent to Enbrel treatment for one and seven years, and the non-adherent group will include patients who did not adhere to Enbrel). There will then be a comparison between both groups; in BSA, PASI, and DLQI scores at baseline, 6-months after Enbrel treatment, and at last visit follow-up after Enbrel treatment.

Patient demographic information (eg, age gender, disease duration) will be analyzed throughout the study.

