8.2. Setting

Patients ≥ 18 years of age will be identified from the local registry at the Dermatology Center in Baghdad Teaching Hospital. Patients diagnosed with moderate-to-severe plaque psoriasis and have been receiving Enbrel treatment for at least 1-year duration are eligible for inclusion in the study.

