8.2.2. Exclusion Criteria

Patients meeting any of the following criteria will not be included in the study:

1. Etanercept use for treatment moderate-to-severe plaque psoriasis less than 1-year duration.
2. Previous use of other biological treatments for any reason.

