8.6. Data Analysis

Categorical covariances will be described by frequency distribution while continuous covariates will be expressed in terms of their mean and standard deviation or median and interquartile range as appropriate. The unadjusted comparisons between groups of the covariates and the outcomes will be evaluated using chi-squared tests for categorical data, while for continuous data, the student's t-test for normally distributed variables and the Kruskall-Wallis test for non-parametric data will be used.

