8.8. Limitations of the Research Methods

Missing data that could lead to bias is an identified limitation in this study.

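### Adherence groups defined over a year or more are compared, unadjusted, on 6-month scores taken inside that period; the 6-month difference cannot be read as an effect of adherence

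*Combined protocol and SAP*

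**What the plan says.** Section 8.1 forms two groups. For the first, "The adherent group will include the patients who were adherent to Enbrel treatment for one and seven years"; for the second, "the non-adherent group will include patients who did not adhere to Enbrel". Neither has a measure or threshold of adherence, and the second has no time window. The section continues: "There will then be a comparison between both groups; in BSA, PASI, and DLQI scores at baseline, 6-months after Enbrel treatment", and also at the last visit. It counts the 6-month score from the start of treatment.

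Section 8.6 gives the only between-group analysis: "The unadjusted comparisons between groups of the covariates and the outcomes will be evaluated using chi-squared tests for categorical data", with a t-test or Kruskal-Wallis test for continuous data. No adjusted model appears anywhere.

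Section 8.2 says that diagnosed patients who "have been receiving Enbrel treatment for at least 1-year duration are eligible for inclusion in the study". Section 8.2.2 excludes "Etanercept use for treatment moderate-to-severe plaque psoriasis less than 1-year duration". The secondary objective in Section 7 reads: "Determine the first year adherence of patients with moderate-to-severe plaque psoriasis".

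Section 8.8 names one limitation: "Missing data that could lead to bias is an identified limitation in this study". No section says how the adherence comparison may be interpreted.

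**The concern.** Group membership depends on what patients did after the 6-month score was recorded. A patient who had cleared well by month 6 may be more likely to carry on as prescribed, and one who had not may lapse. The groups would then differ at 6 months even if adherence had no effect.

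The entry rule adds a second distortion. Non-adherent patients who responded poorly and stopped before 1 year are not in the data, so the remaining non-adherent patients may look better than non-adherent patients in general. This pulls the difference the other way.

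An unadjusted test cannot separate these two mechanisms from any effect of adherence in months 0 to 6. As the plan stands, the report would give 6-month group differences with p-values and nothing to say what they can mean. Section 6 speaks of the value of adherence, so a reader could easily take such a difference as evidence that adherence improved the scores.

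**Working it through.** The plan gives no figure to reproduce. It states a study size of approximately 400 with no alpha, power, effect size, SD or group split. The check has two parts.

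**1. Timing.** The wording of the adherent period is ambiguous, but its shortest reading is 12 months. The score is taken at month 6, so at least 12 - 6 = 6 months, or 6/12 = 50% of the grouping period, comes after the score. On a seven-year (84-month) reading it is 84 - 6 = 78 months, or 78/84 = 93%.

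**2. Illustration with no adherence effect.** Every input here is assumed; none comes from the documents.

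- z = 6-month improvement in SD units, distributed N(0,1).
- Probability of being adherent: p(z) = logit⁻¹[ln(0.7/0.3) + ln(OR)·z]. This gives about 70% adherent; OR is the odds ratio for adherence per SD of improvement.
- All adherent patients reach 1 year. Non-adherent patients reach it with probability k(z) = logit⁻¹[ln(r/(1-r)) + ln(2)·z]. Here r is the share of average (z = 0) non-adherent patients who reach 1 year, and their odds double per SD of improvement. Without selection, k(z) = 1.
- Difference, adherent minus non-adherent: D = E[z·p]/E[p] - E[z·(1-p)·k]/E[(1-p)·k].

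Numerical integration gives the following, in SD; differences are taken before rounding:

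| | OR 1.25 | OR 1.5 | OR 2.0 |
|---|---|---|---|
| Mean z, adherent | 0.067 | 0.120 | 0.200 |
| Mean z, non-adherent, no selection | -0.154 | -0.272 | -0.431 |
| **D, no selection** | **0.22** | **0.39** | **0.63** |
| Mean z, non-adherent, r = 50% | 0.170 | 0.057 | -0.106 |
| **D, r = 50%** | **-0.10** | **0.06** | **0.31** |
| Mean z, non-adherent, r = 80% | -0.004 | -0.117 | -0.275 |
| **D, r = 80%** | **0.07** | **0.24** | **0.48** |

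The true effect is zero in every cell. For OR 1.25, for example, D without selection is 0.067 - (-0.154) = 0.22, and with r = 50% it is 0.067 - 0.170 = -0.10. Simulation of the same model agrees to within about 0.01.

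Early response driving later adherence pushes the difference up, and selection at 1 year pushes it down. Changing r from 50% to 80% is enough to turn -0.10 into 0.07. The plan supplies neither OR nor r.

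**The case against.** The best defence is that the plan claims no causal effect of adherence. The secondary objective only sets out to determine first-year adherence, Section 8.6 openly calls the comparisons unadjusted, and no hypothesis or alpha is attached to the contrast. All of that stands. A reader might infer from Section 6 that the sponsor intends a causal conclusion; the text makes that reading foreseeable but does not state it. What remains is that Section 8.6 tests outcomes between these groups, and nothing in the plan says the 6-month result is descriptive.

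Four other stronger readings are also unsupported:

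- *The comparison is worthless.* It is not. It can describe how the groups differed at 6 months, or show whether early response goes with later adherence. Only a conclusion about the effect of adherence is blocked.
- *The bias is large, or runs in a known direction.* The documents give nothing from which to estimate it. Near-zero and reversed differences depend heavily on how many non-adherent patients reach 1 year: with doubled odds they appear at r = 50%, while at r = 80% all three differences are positive.
- *The 1-year rule empties the non-adherent group.* Non-adherence is undefined, so the group could hold patients who adhered poorly but stayed on treatment for a year, or who stopped later. The rule and the group need reconciling; they are not shown to be incompatible.
- *The main efficacy result is undermined.* The primary objective compares each score with baseline and does not use these groups.

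The entry rule does not rescue the comparison. It removes early stoppers but leaves poor adherence within year 1, and it adds selection.

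**Conclusion.** The concern holds for the effect of adherence and no further. At least half of the adherence period follows the 6-month score on any reading of Section 8.1, the planned tests are unadjusted, and entry is conditional on 1 year of treatment. The 6-month difference between groups therefore does not estimate an effect of adherence.

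The timing argument rests on the text alone. The sizes do not: a spurious difference of roughly -0.10 to 0.63 SD is the range across the illustrated settings, not an estimate for this registry, and other inputs would widen or narrow it. The point is worth correcting, but it concerns a secondary comparison.

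**What to change.** 1. **Sections 8.1 and 8.6, 6-month scores.** Present baseline and 6-month scores by adherence group as descriptive, and do not report the 6-month difference as an outcome of adherence. If an analysis is wanted, reverse it: model adherence on 6-month response, adjusted for baseline score (for example, by logistic regression), and state that the result describes only patients treated for at least 1 year.
2. **Section 8.6, last visit.** Replace the unadjusted test with ANCOVA on the baseline score, which is already collected. State that confounding by early response and selection by the entry rule remain.
3. **Sections 7, 8.1 and 8.2.** Reconcile the non-adherent group and the first-year adherence objective with the 1-year eligibility rule. Section 5 planned the end of data collection for 01 October 2020, and the July 2021 amendments in Section 4 aligned dates with a study report. Any definition set after data collection should be marked post hoc.
4. **Section 8.8.** Add a limitation such as: *The adherence groups cover a period that runs past the 6-month assessment and include only patients with at least 1 year of treatment; group differences at 6 months do not estimate an effect of adherence.*

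Items 1, 2 and 4 use the scores and the grouping the plan already relies on. The cost is one fewer inferential comparison and a little more analysis. Item 3 may show that the registry cannot support a clean definition, in which case the report should say so.

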8.2. Setting

Patients ≥ 18 years of age will be identified from the local registry at the Dermatology Center in Baghdad Teaching Hospital. Patients diagnosed with moderate-to-severe plaque psoriasis and have been receiving Enbrel treatment for at least 1-year duration are eligible for inclusion in the study.

8.2.1. Inclusion Criteria

Patients must meet each of the following inclusion criteria to be eligible for inclusion in the study:

1. Confirmed diagnosis of moderate-to-severe plaque psoriasis and receiving etanercept treatment for a minimum duration of 1 year.
2. Age ≥ 18 years old.
3. No history of using a biological treatment, other than etanercept, for treatment of moderate to severe plaque psoriasis or any other reason.

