8.4. Study Size

This study will include approximately 400 patients from the local registry that meet the inclusion criteria detailed in that described previously.

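### Entry requires at least one year on Enbrel, so the first-year adherence objective can describe only patients treated for at least a year; permanent year-one stoppers are never counted

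*Combined protocol and SAP*

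**What the plan says.** Section 7 gives one secondary objective: "Determine the first year adherence of patients with moderate-to-severe plaque psoriasis on a Enbrel treatment".

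Three places set the same entry condition. Section 8.2 says that patients who "have been receiving Enbrel treatment for at least 1-year duration are eligible for inclusion in the study". Inclusion criterion 1 in section 8.2.1 requires patients to be "receiving etanercept treatment for a minimum duration of 1 year". Exclusion criterion 1 in section 8.2.2 removes "Etanercept use for treatment moderate-to-severe plaque psoriasis less than 1-year duration". Section 8.4 applies the condition to the whole sample: "This study will include approximately 400 patients from the local registry that meet the inclusion criteria".

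Section 8.1 splits these patients by adherence. Its first group is set out as follows: "The adherent group will include the patients who were adherent to Enbrel treatment for one and seven years". For the comparison group it says only that "the non-adherent group will include patients who did not adhere to Enbrel". It gives no measure, threshold, gap rule or time window. Section 6 speaks of adherence to the treatment regimen. The analysis in section 8.6 does not bring back patients treated for less than a year, and section 8.8 names missing data as the only limitation.

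**The concern.** Entry to the cohort depends on time on drug, and time on drug in year one is either the outcome of the secondary objective or closely tied to it. Permanent year-one stoppers are the patients most plainly lost to treatment in that year, and no section readmits them.

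A reader of the result would naturally take a first-year adherence figure as describing what happens once patients start Enbrel. Section 6 offers the study as local evidence on Enbrel use, including adherence, which encourages that use. This cohort can give adherence only among patients who reached one year of treatment. Leaving out stoppers by rule is selection, so the missing-data statement in section 8.8 does not cover it.

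**Working it through.** **Inputs from the documents.** Minimum treatment duration 1 year (sections 8.2, 8.2.1, 8.2.2); about 400 patients, all meeting the criteria (section 8.4); objective of first-year adherence (section 7). The plan states no adherence rate, stopping rate or sample-size derivation, so it has no figure to reproduce.

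**Assumed inputs, for illustration only.** f = share of starters who stop in year one, 0.10 to 0.40. a = adherence among included patients, 0.70 to 0.90. s = on-drug adherence of stoppers, within 0.10 of a either way. r = share of stoppers who resume and accumulate a year, 0.10 to 0.50 (step 5 only; elsewhere stopping is permanent).

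1. **Patients left out.** Starters behind 400 included = 400/(1 − f). At f = 0.10 this is 444, so 44 are left out. At f = 0.40 it is 667, so 267 are left out.

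2. **Regimen-taking, stoppers counted as non-adherent.** The included cohort shows a; all starters have a(1 − f); the overstatement is a·f. The lowest case is 0.70 × 0.10 = 7 points (70% against 63%). The highest is 0.90 × 0.40 = 36 points (90% against 54%). The non-adherent group is not empty: 400(1 − a) = 120 at a = 0.70 and 40 at a = 0.90.

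3. **Regimen-taking, scored only while on drug.** All starters have (1 − f)a + f·s, so the difference is f(a − s). With s within 0.10 of a, this is −4 to +4 points at f = 0.40 and −1 to +1 at f = 0.10. The direction is unknown.

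4. **Continuous persistence, continuous year required.** P(on drug through year one | at least one year on drug) = 1. The cohort shows 400 of 400 whatever the truth, against 1 − f = 90% to 60%, so the overstatement is 10 to 40 points and the year-one non-adherent group is empty. Eligibility fixes this value, so it has no sampling uncertainty and no confidence interval should be attached to it.

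5. **Continuous persistence, accumulated year accepted.** The criteria do not say that the year must be unbroken. The cohort shows (1 − f)/(1 − f + f·r) against 1 − f:
   - f = 0.10, r = 0.10: 98.9% against 90%, 8.9 points over, 4 non-adherent of 400.
   - f = 0.10, r = 0.50: 94.7% against 90%, 4.7 points over, 21 non-adherent.
   - f = 0.40, r = 0.10: 93.8% against 60%, 33.8 points over, 25 non-adherent.
   - f = 0.40, r = 0.50: 75.0% against 60%, 15.0 points over, 100 non-adherent.

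   Permanent stoppers are still absent.

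The size and, in step 3, the direction depend on the definition. The condition on one year of treatment is present in every step.

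**The case against.** The best defence is that the plan does not mean persistence. Section 6 refers to the treatment regimen, and section 8.1 plans a non-adherent group within the same 400 or so patients, which makes little sense if everyone is adherent by rule. On that reading the objective can be estimated. Section 7 also never claims to cover everyone who started Enbrel; it speaks of patients on the drug, and objectives are read together with eligibility, which states the one-year condition openly three times. The objective is secondary and descriptive, and every size above rests on assumed rates.

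Most of this stands. A reader might infer that the adherence result must be 100% and the objective is void. The documents do not support that: it follows only if adherence means persistence over a continuous year, which is the reading that sections 6 and 8.1 favour least. Nor do they support saying that the figure is too high on every definition; if adherence is scored only on drug, it could err either way.

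What remains is narrower. Adherence is undefined, so persistence is not ruled out. Even on the favoured reading, section 7 omits the condition that limits the figure, and section 8.8 omits the selection.

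**Conclusion.** The concern holds as a conditional-denominator problem. The cohort can give first-year adherence only among patients treated for at least one year, and the plan neither says so in the objective nor lists it as a limitation. On the regimen-taking reading, the figure is usable once the condition is stated. Under the assumed 10% to 40% stopping and 70% to 90% adherence, it would exceed the all-starters figure by 7 to 36 points if stoppers count as non-adherent. If persistence over a continuous year is meant, the figure carries no information.

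The structural point rests on the text alone; the sizes rest on rates the documents do not give. Severity is should-fix, rising to must-fix if adherence means persistence.

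**What to change.** **Option 1: change the denominator, for the secondary objective only.**
- Use all registry adults with moderate-to-severe plaque psoriasis, no other biologic before the first Enbrel dose, and a first dose at least 12 months before the actual data-export date, regardless of time on drug.
- State that date. Section 5 gives only a collection window, 1 September to 1 October 2020.
- Date the biologic history to before the first dose. Inclusion criterion 3 gives no date, so stoppers who later switched biologic could otherwise be lost.
- State one adherence measure and count permanent stopping before month 12 as non-adherent.
- Give a rule for unknown month-12 status, such as time to discontinuation with censoring, or best-case and worst-case bounds.
- Report the estimate with a 95% CI.

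**Option 2: change the objective.** If the registry does not hold early stoppers, or a new export is not feasible, restate the objective as adherence among patients treated for at least one year (or withdraw it if persistence is meant) and list the selection in section 8.8.

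**In either case, the section 8.1 comparison.** Section 8.1 states: "There will then be a comparison between both groups; in BSA, PASI, and DLQI scores at baseline, 6-months after Enbrel treatment". If this stays in the one-year cohort, do not define its groups by 12-month persistence, which would empty or nearly empty the non-adherent arm. Use a measure that can vary there, such as regimen-taking. Label the comparison descriptive and conditional on one year of treatment, since adherence may itself depend on earlier response, including the 6-month scores.

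**Cost.** Option 1 needs a protocol amendment, IRB/IEC approval (section 9.3) and a further registry export after data collection closed; the documents do not show whether early stoppers are held. Option 2 needs no new data, only rewording of section 7 and one added limitation, though section 9.3 still requires approval of the amendment. The primary-analysis population is unchanged.

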8.2.2. Exclusion Criteria

Patients meeting any of the following criteria will not be included in the study:

1. Etanercept use for treatment moderate-to-severe plaque psoriasis less than 1-year duration.
2. Previous use of other biological treatments for any reason.

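### The 6-month primary contrast uses only patients who stayed on etanercept for at least a year, so it is likely to overstate improvement in all starters if lack of effect drives early stopping

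*Combined protocol and SAP*

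**What the plan says.** Section 7 puts the aim broadly: "This study aims to evaluate the efficacy of Enbrel as a biological treatment in moderate-to-severe plaque psoriasis patients in Iraq". Its primary objective sets baseline scores against "scores after 6 months of initiation of treatment" and against the last visit. Neither statement is limited to long-term users.

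Eligibility is narrower, and the plan says so three times. Section 8.2 admits patients who "have been receiving Enbrel treatment for at least 1-year duration are eligible for inclusion in the study". Section 8.2.1 requires "receiving etanercept treatment for a minimum duration of 1 year". Section 8.2.2 excludes "Etanercept use for treatment moderate-to-severe plaque psoriasis less than 1-year duration". Section 8.4 then states: "This study will include approximately 400 patients from the local registry that meet the inclusion criteria". There is no separate analysis set for the 6-month contrast.

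Nothing elsewhere deals with the selection. Section 8.6 offers descriptive summaries and unadjusted between-group tests. Section 8.8 names missing data as the only limitation. Section 8.1 mentions a non-adherent group, but does not define it in a way that would bring back patients with under a year of use.

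**The concern.** Take a patient with a poor month-6 score who stops at month 8. The score exists and belongs to the period the contrast describes, yet the patient is removed by something that happened later. A patient who stops at month 4 never reaches the assessment and is removed as well. The 6-month result is thus conditioned on the future: it describes starters already known to have continued to 12 months.

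If poor response is a reason for stopping, those removed are disproportionately the poor responders, and the remaining mean is higher than the mean among all starters. The error does not shrink with more patients, and a confidence interval from 400 patients does not reflect it.

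The 6-month score matters because it is the only post-baseline primary measurement at a fixed time; the last visit varies by patient. Section 6 also says that there are no published local data and few regional data, so readers would have little with which to correct the figure.

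**Working it through.** **Plan's own figure.** The approximate 400 in section 8.4 cannot be reproduced, because no alpha, power, effect size or SD is given. It is an expected count of eligible records. The number of starters behind it would be 400/(1 − d), where d is the share stopping before 1 year: 445, 500, 572 or 667 for an assumed d of 10%, 20%, 30% or 40%.

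**Identity.** Let m_stay and m_stop be the mean 6-month improvements of patients who did and did not reach 1 year. The mean in all starters is (1 − d) × m_stay + d × m_stop, so

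error = m_stay − mean in all starters = d × (m_stay − m_stop).

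The documents supply neither d nor the gap; both are assumptions below.

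**Plain grid.** With d from 10% to 40% and a gap from 10 to 40 points of PASI improvement, the error runs from 0.10 × 10 = 1 point to 0.40 × 40 = 16 points. With no gap it is 0. If stoppers did 10 points better, it is −1 to −4 points.

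**A response-driven model (assumed).** Percentage PASI improvement at month 6 in all starters is N(65, 30) capped at 100. A patient below 50% improvement stops within the year with probability a, any other patient with probability b.

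- Share below 50%: Φ((50 − 65)/30) = 0.3085.
- Mean improvement: 30.77 in that group and 77.67 in the rest.
- All starters: 0.3085 × 30.77 + 0.6915 × 77.67 = 63.20.
- Share stopping: d = 0.3085a + 0.6915b.
- Mean in stayers: [0.3085(1 − a) × 30.77 + 0.6915(1 − b) × 77.67] / (1 − d).

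| a | b | d | Mean in stayers | Error (points) |
|---|---|---|---|---|
| 0.30 | 0.10 | 16.2% | 65.59 | 2.39 |
| 0.30 | 0.05 | 12.7% | 66.06 | 2.87 |
| 0.60 | 0.10 | 25.4% | 69.91 | 6.71 |
| 0.60 | 0.05 | 22.0% | 70.25 | 7.05 |
| 0.20 | 0.10 | 13.1% | 64.35 | 1.15 |
| 0.15 | 0.15 | 15.0% | 63.20 | 0 |
| 0.05 | 0.15 | 11.9% | 62.06 | −1.14 |

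The first four rows are the corners of the range a = 0.3 to 0.6, b = 0.05 to 0.10. The last three show weak, absent and reversed dependence on response.

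**Comparison with sampling error.** The SD of the capped distribution is 26.9, so the 95% half-width at n = 400 is 1.96 × 26.9/√400 = 2.64 points. Across the four corners the error is 2.39/2.64 = 0.9 to 7.05/2.64 = 2.7 half-widths.

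The model gives every patient a month-6 value, so it does not describe those who stopped before month 6.

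**The case against.** The strongest reply is that the cohort is disclosed. Section 8.2 defines the study population as users of at least 1 year, section 8.4 sizes the study on them, and section 6 frames the interest around long use. For that population this rule does not bias the 6-month mean. That stands: the defect is a mismatch between the population in section 7 and the one analysed. It is still a defect, because section 7 draws no such limit and section 8.8 does not mention the selection.

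Second, a reader might infer that the 6-month improvement *is* overstated and that the error can run only one way. The documents do not support this. They give no number of starters, no first-year stopping rate, no reasons for stopping and no scores for early stoppers. Overstatement is the expected direction when lack of effect drives stopping, but zero or negative error is equally compatible with the text. The study as designed cannot show which applies, since it leaves out the patients who would reveal it.

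Third, feasibility. Excluding short users does not prove that the registry holds their month-6 scores, and section 5 ended data collection on 01 October 2020. This stands too, and it is why the fix needs a fallback.

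Finally, the same duration rule affects the secondary objective, "Determine the first year adherence of patients with moderate-to-severe plaque psoriasis", by removing first-year discontinuers. That is a separate consequence, but one revision of section 8.2 could address both.

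**Conclusion.** The structural point holds on the text alone: membership of the 6-month primary analysis is decided by events after, or instead of, the 6-month outcome, and the plan neither corrects nor acknowledges this. As an estimate for all patients who start etanercept, the 6-month improvement is likely to be overstated if lack of effect drives early stopping.

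No figure for the size can be taken from the documents. The range of about 2.4 to 7 points rests wholly on the assumed response distribution and stopping probabilities and should be read as illustrative. It shows that the error could match or exceed sampling error, not that it does.

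**What to change.** For the 6-month contrast only, drop the duration part of inclusion criterion 1 and exclusion criterion 1. Include every registry patient who started etanercept at least 6 months before data cut-off and meets the other criteria as written, including the bar on other biologics. Use the month-6 score even if the patient later stopped.

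Report how many stopped before month 6, how many stopped before 1 year, and how many have no month-6 score. Add a sensitivity analysis for those without a score, for example assuming no change from baseline. That assumption is deliberately simple and should be labelled as such. Keep the at-least-1-year cohort for the last-visit contrast and as a supplementary 6-month analysis.

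If the registry or the closed extract does not hold early stoppers, label the result *6-month change among patients who went on to complete at least 1 year*, restrict the efficacy conclusion to them, and add the selection to section 8.8.

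The cost of the full fix is one wider registry extraction, made after the stated end of data collection, plus short additions to sections 8.2 and 8.6, and probably a slightly less favourable 6-month figure. The fallback needs only changes of wording.
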